### **5.13.5.2 ECG Overall Interpretation**

The ECG interpretation (normal, abnormal not clinically significant [NCS], abnormal clinically significant [CS]) will be summarized for each time period and overall. Within each time period if a subject has at least 1 clinically significantly abnormal record, this subject will be counted as having the incidence for that time period. The ECG parameters for these subjects will be presented in a data listing.

The ECG interpretation will also be provided in a listing with date and time of collection and additional comments.

### **5.13.6 UPDRS Parts II and III**

The Parts II+III UPDRS score will be derived as the sum of the 40 items from activities of daily living (Part II, 13 items) and motor examination (Part III, 27 items), with a range of 0 to 160 (for each item the score ranges from 0 (normal or absent of symptom) to 4 (worst condition)).

For UPDRS Parts II+III, Part II, and Part III scores, the highest (worst) measurement will be used for generating the population summary statistics within each time period. In addition, for the overall study period, the last and the highest measurement from each subject will be summarized.

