3. STUDY DESIGN

3.1 Overall Study Design

Pimavanserin will be administered once daily at a fixed dose level of 40 mg. The study will be conducted on an outpatient basis.

Subjects who have completed the treatment period of a previous blinded study of pimavanserin in PDP subjects and who may, in the opinion of the Investigator, benefit from continued treatment with pimavanserin will be enrolled in this study for safety evaluation. Subjects may be enrolled in this study as early as the last visit of the treatment phase of the previous study OR up to 28 days following completion of the treatment period.

Subjects will be required to visit the clinic on Week 2 (Day 14 ± 3 days), Month 1 (Day 28 ± 3 days), Month 3 (Day 84 ± 7 days), Month 6 (168 days ± 7 days), Month 9 (252 days ± 7 days), Month 12 (336 days ± 7 days) and every six months thereafter (every 168 days ± 7 days). Unscheduled clinical evaluations may occur at anytime if deemed appropriate by the Investigator. If the subject terminates the study at any time other than a planned visit the subject will be required to visit the clinic for an end-of-study evaluation.

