12.2 Efficacy Analysis

No formal statistical analysis is currently planned for the clinical rating scales (SAPS, UPDRS, CGI-I, CGI-S and Caregiver Burden Scale) recorded in this study; however, results for the safety population will be summarized with descriptive statistics at each study visit.

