### **3.2 Clinical Rating Scales**

The Caregiver Burden Scale, Clinical Global Impression-Severity (CGI-S), Clinical Global Impression-Improvement (CGI-I), and Unified Parkinson's Disease Rating Scale (UPDRS; a safety measure) parts II and III will be administered at all scheduled post-baseline visits. The Scale for the Assessment of Positive Symptoms (SAPS) will be administered at Month 1 only.

The Non-Motor Symptom scale (NMSS; a safety measure) for PD was initially collected in this study but was discontinued with amendment 6. Results will be presented in a data listing but will not be summarized.

The Resource Utilization in Dementia (RUD)-Lite (health economics outcome measure) will be collected at baseline (all subjects had a baseline RUD-Lite performed), Month 12, every 6 months thereafter, and at end of study.

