## **5 STATISTICAL CONSIDERATIONS**

### **5.1 General Statistical Procedures**

Statistical summaries will be generated using SAS® software, version 9.3 or higher. No formal statistical tests will be conducted. Unless otherwise specified, continuous parameters will be summarized using the following descriptive statistics: number of observations, mean, median, standard deviation (SD), standard error of the mean (SEM), minimum and maximum. Categorical parameters will be summarized using the number and percentage of subjects in each level of a category.

Descriptive statistics will be presented using a significant figure rule: the minimum and maximum will have the same number of significant figures as the data; the mean and median will have one more significant figure than the data being summarized; the SD and SEM will have two more significant figures than the data being summarized; and the sample size (n) will be reported as an integer.

Unless otherwise indicated, descriptive statistics will be reported for observed cases only and missing data will not be imputed. Missing observations will not be taken into account when calculating frequencies, unless otherwise indicated. By-visit summary tables will include all available subjects' data up to 4 years (192 weeks) on study, and any data beyond that point will be summarized in a single visit (>192 weeks). For laboratory, vitals, and ECGs by time period summaries an additional last assessment will be included.

Data listings will include all data for all subjects. Listings will present data sorted by site number, subject identification, study day, and visit (both nominal and derived, if applicable), unless otherwise specified. If a listing includes a derived visit, then in those cases where a subject has more than one result in the derived visit window the result that is used for analysis will be flagged in the listing.

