#### 5.4.2 Summary Time Periods for Safety Results

For safety assessments (AEs, laboratory tests, vital signs, ECG data, UPDRS II+III and physical examinations), the data summary will be based on chronological time periods as defined in [Table 2](#). Rules for determining the analysis values within each time period are detailed in [Section 5.13](#).

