### **5.11.2 Caregiver Burden Scale**

The Caregiver Burden Scale (CBS) is a 22-item questionnaire completed by the subject’s caregiver. Each item is rated on a scale of 0 - 4 where 0 = never, 1 = rarely, 2 = sometimes, 3 = frequently, 4 = nearly always. The total score of the Caregiver Burden Scale will be derived as the sum of the 22 items, with a possible range of 0 to 88. The total score and change from baseline will be summarized by visit. The data will also be summarized within each geographic area (North America and outside North America).

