## **6 DEVIATIONS FROM PROTOCOL PLANNED ANALYSIS**

Section 10.1 of the Protocol specified that all analyses would be performed SAS® using version 8. However, SAS® version 9.3 (or higher) will be used for all statistical analyses.

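### By-period UPDRS rests only on each subject's worst score, an unlisted departure from the Protocol's by-visit plan, and its mean would step up after Month 6 through visit count even with no true change

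*SAP*

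**What the plan says.** UPDRS is collected often enough to describe a time course. SAP 3.2 says that "parts II and III will be administered at all scheduled post-baseline visits", and Protocol 7.2 gives the same visits plus End-of-Study.

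The two documents summarize it differently:

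- **Protocol 12.2** names SAPS, UPDRS, CGI-I, CGI-S and the Caregiver Burden Scale together and says "results for the safety population will be summarized with descriptive statistics at each study visit".
- **SAP 5.4.2** places UPDRS with the safety data: "UPDRS II+III and physical examinations), the data summary will be based on chronological time periods".
- **SAP 5.13.6** then fixes the analysis value: "the highest (worst) measurement will be used for generating the population summary statistics within each time period". The last score is added once, for the whole study. No lowest, by-visit or change-from-baseline summary of UPDRS is stated.
- **SAP 5.11** keeps by-visit summaries for CGI-S, CGI-I and Caregiver Burden. For the last of these, "The total score and change from baseline will be summarized by visit". SAPS is taken at Month 1 only.
- **SAP Section 6** has a single entry, about software. It begins "Section 10.1 of the Protocol specified that all analyses would be performed" and goes on to the SAS version.

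Of the repeated scales named in Protocol 12.2, only UPDRS loses its by-visit summary, and the SAP does not record this as a departure.

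**The concern.** A maximum depends on how many values it is taken over. If the number of scheduled visits differs between periods, the mean worst score differs too, even when every subject's true level is constant. The SAP Table 2 periods do not hold equal numbers of UPDRS visits, and the count doubles at the six-month boundary.

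Protocol 1.3 rests the case for the drug on reducing psychosis without loss of motor function. The worst-score table would be the only planned display of the motor score over time. With stable patients it can show a low value at >3–6 months and then a lasting rise, which invites a reading of late motor deterioration. A reader could not separate that artefact from real progression.

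**Working it through.** There is no plan figure to reproduce. SAP 2.4 gives no sample size calculation, and neither document gives an SD or correlation for UPDRS.

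**1. Scheduled visits per period.** Visit days and allowances are from Protocol 3.1, periods from SAP Table 2.

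| Period (study days) | Scheduled visits, Amendment 6 | Count |
|---|---|---|
| First 4 weeks (2–28) | Day 14; Month 1 if on Day 25–28 | 1 or 2 |
| 1–3 months (29–91) | Month 1 if on Day 29–31; Day 84 | 1 or 2 |
| >3–6 months (92–183) | Day 168 (161–175) | 1 |
| >6–12 months (184–365) | Days 252 (245–259), 336 (329–343) | 2 |
| >1–2 years (366–730) | Days 504, 672 | 2 |
| >2–3 years (731–1095) | Days 840, 1008 | 2 |
| >3–4 years (1096–1461) | Days 1176, 1344 | 2 |

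Month 1 straddles the Day 28/29 cut: 4 of its 7 allowed days fall in the first period and 3 in the second. On SAP Table 1 target days, which are one day later, the first two target counts change from 2 and 1 to 1 and 2. The last of the 15 allowed Month 3 days (Day 92) then also falls in >3–6 months. The change from one to two target visits after Month 6 is the same on either numbering.

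**2. Expected excess of the higher of two scores.** Let σ be the within-subject SD and r the correlation between the two visit errors, with no true change:

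E[max] − true level = σ√((1 − r)/π)

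For r = 0 this is 0.564σ. For r = 0.5 it is 0.564 × 0.707 = 0.399σ. With a single visit it is zero, so these are also the steps from >3–6 to >6–12 months.

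| Assumed σ (points) | r = 0 | r = 0.5 |
|---|---|---|
| 3 | 1.69 | 1.20 |
| 5 | 2.82 | 1.99 |
| 7 | 3.95 | 2.79 |

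**3. Missed visits.** If each of the two visits is attended with probability 0.8, the share of contributing subjects with two values is 0.64/0.96 = 0.667. At σ = 5 the step is 0.667 × 2.82 = 1.88 (r = 0) or 0.667 × 1.99 = 1.33 (r = 0.5).

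**4. Whole profile.** This was simulated with 200,000 subjects, no true change, σ = 5, full attendance and visit days uniform over the allowed days. Mean worst score minus true level, First 4 weeks to year 4:

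- independent errors: 1.6, 1.2, 0.0, 2.8, 2.8, 2.8, 2.8
- correlation 0.5 between successive visits: 1.1, 0.9, 0.0, 2.0, 2.0, 2.0, 2.0

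The first two values agree with step 2: 4/7 × 2.82 = 1.61 and 3/7 × 2.82 = 1.21.

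**5. Different assumptions, with dropout.** Taking instead a total SD of 10 to 20 points and a correlation between scores of 0.95 to 0.70, the step runs from 10√(0.05/π) = 1.26 to 20√(0.30/π) = 6.18. A simulation of 400,000 subjects added non-informative dropout and an End-of-Study score (SD 15, correlation 0.9). The step was 2.67 with no dropout, 2.51 at an annual hazard of 0.35 and 2.37 at 0.6. Dropout shrinks it but does not remove it.

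**6. Earlier three-monthly schedule (SAP 2.2).** Year 2 then holds four visits (Days 420, 504, 588, 672) and year 3 has five target days. The expected maximum of four or five independent values is 1.03 or 1.16σ above the true level. At σ = 5, year 2 is inflated by 1.03 × 5 = 5.15 points on that schedule against 2.82 on Amendment 6.

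**7. By-visit alternative.** Each scheduled visit, over all its allowed days, falls in exactly one SAP Table 1 window, and each post-baseline window through Week 192 holds one. In the simulation of step 4 the by-visit means stay within 0.02 of zero throughout.

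**The case against.** The strongest reply is that worst-case reporting is a deliberate safety choice. SAP 3.2 labels UPDRS a safety measure, laboratory, vital-sign and ECG data are also summarized by extremes within period, and the text says openly that the highest score is the worst. On this view the rule may overstate worsening but cannot hide it. The first part explains the choice but does not list it as a departure from the Protocol. The other safety measures also get the lowest value and a stated change from baseline. The last part does not hold for comparisons over time: where the visit count falls, as between the first 4 weeks and >3–6 months for many subjects, the artefact runs downward and can offset real worsening.

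It can also be said that UPDRS matters less than claimed. Protocol 6.1 does not name it among the measures of the primary objective, no formal tests are planned, and adverse events and physical examinations are tabulated by period. This stands as a limit on severity, but none of those tables gives a time course of the motor score.

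Several limits on the numbers also stand. The point size rests on an assumed SD, and 2.0 to 2.8 points is under 2% of a 0–160 scale. The documents give no threshold for meaningful change. The flat profile from >6–12 months onward applies to full attenders on the Amendment 6 schedule only. Protocol 1.2 reports 77 subjects with more than 12 months of treatment by May 2010, so some had three-monthly visits. The early part of the profile depends on day numbering. An observed step would also contain progression, selective dropout and unscheduled visits. Finally, Protocol 12.2 does not promise change from baseline, so that part of the fix goes beyond restoring the Protocol.

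**Conclusion.** The concern holds. The by-period UPDRS summary departs from Protocol 12.2 without being listed, and it builds in a rise between >3–6 and >6–12 months that needs no change in any patient. The direction is certain whenever scores vary within subject and the scheduled visits are attended. The size is 0.40 to 0.56 within-subject SD for error correlations of 0.5 to 0, or +2.0 to +2.8 points at an assumed SD of 5. With 80% attendance per visit it is +1.3 to +1.9 points.

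This should be corrected before the tables are final. It does not undermine the primary safety objective, and the overall last score and the baseline summary are not inflated by visit count. Those two summaries give endpoints, though, and not a course.

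**What to change.** - **SAP 5.4.1:** add UPDRS II+III, II and III to the scales named there, so that the Table 1 windows, the nearest-to-target and tie rules, and the limit of three days after the last dose apply.
- **SAP 5.13.6:** add a by-visit summary of each score with n, observed value and change from the core-study baseline of SAP 5.9.1, one value per subject per window. Name it as the display of mean change. Keep the worst-score period table as the worst-case display and leave the Table 2 boundaries as they are.
- **SAP Section 6:** list the period-based worst-score UPDRS summary as a departure from Protocol 12.2.

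The cost is a few tables (three scores, observed and change), two text edits and one line in Section 6. Windows, tie rule, baseline and the handling of data beyond 192 weeks (SAP 5.1) already exist, and no new data are needed. By-visit means remain open to dropout, as the period table is, so n per window must be shown. In a single-arm study of a progressive disease they describe the course and do not isolate a drug effect.

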#### **5.13.7 Non-Motor Symptom Scale**

The Non-motor Symptoms Scale (NMSS) is a 32 item scale that measures non-motor symptoms of PD. NMSS contains nine domains: cardiovascular including falls (2 items), sleep/fatigue (5 items), mood/cognition (7 items), perceptual problems/hallucinations (3 items), attention/memory (3 items), gastrointestinal tract (3 items), urinary (3 items), sexual function (2 items), and miscellaneous (4 items). Each item has a severity rating (0 to 3) and a frequency rating (1 to 4). The score for each item is the product of severity and frequency with a range of 0 to 12. NMSS total score is the sum of the 32 item scores, ranging from 0 to 384.

The NMSS individual item scores, along with the total score, will be presented in a data listing by domain. The NMSS was initially collected during this study, but was discontinued with Amendment No. 6.

#### **5.13.8 Physical Examination**

Physical examination results (normal, abnormal) will be summarized in a frequency table by body system by time period.

Data listings will include date and time of evaluation, any abnormal findings within each body system, clinical significance, and a comment describing the abnormality and clinical significance of the abnormality.

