Physical Exam ³	X	X	X	X	X	X	X	X
Clinical Labs	X	X	X	X	X	X	X	X
Serum Pregnancy Test	X			X	X	X	X	X
Plasma PK Sample ⁴		X	X	X	X	X	X	X
Caregiver Burden Scale		X	X	X	X	X	X	X

¹ Subjects that enroll in this study within one week of completion from a previous blinded study of pimavanserin in will only be required to sign an informed consent form, complete an update to the medical history that was performed during the screening and baseline visit of the previous study, complete the Baseline RUD-Lite, and receive study drug during the baseline visit. Subjects that enroll greater than one week of completion from the previous blinded study will be required to complete ALL baseline assessments. All assessments are to be performed PRIOR to investigational drug administration.

² The medical history to be taken at baseline will be an update to the medical history taken during the screening and baseline visits of the previous study. Any AEs that occur after the informed consent is signed and before the first dose of investigational drug is taken are to be recorded in the updated medical history and NOT in the AEs log.

³ The physical examination performed on Week 2, Month 1, Month 3, Month 6, Month 9, Month 12 and every 6 months thereafter will be an update to the full physical examination conducted during either the last visit of the previous study or at Baseline of this study.

Visit	1	2	3	4	5	6	7	8
	Baseline (Day 1)	Week 2 (Day 14 ± 3 days)	Month 1 (Day 28 ± 3 days)	Month 3 Day 84 ± 7days	Month 6 Day 168 ± 7days	Month 9 Day 252 ± 7days	Month 12 (Day 336 ± 7 days) AND every 6 months thereafter (168 days ± 7 days)	End-of-Study (if subject withdraws or is terminated from the study)
SAPS ⁵			X					
UPDRS Parts II & III ⁶		X	X	X	X	X	X	X
CGI-S and CGI-I ⁷		X	X	X	X	X	X	X
Adverse Events ⁸	X	X	X	X	X	X	X	X
RUD Lite ^{1,9}	X						X	X
Prior/Con Meds	X	X	X	X	X	X	X	X
Investigational Drug Administration ¹⁰	X	X	X	X	X	X	X	

⁴ Plasma samples for determination of pimavanserin levels are to be taken PRIOR to investigational drug administration on study days; on study visit days the subject should NOT take the day's dose of investigational drug at home. They should wait until they are at the clinical site.

⁵ Scale for the Assessment of Positive Symptoms (SAPS) may be administered by a Central Rater Service, [REDACTED]

⁶ Unified Parkinson's Disease Rating Scale (UPDRS)

⁷ Clinical Global Impression scale-Severity (CGI-S) and Clinical Global Impression scale-Improvement (CGI-I)

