6.2.2. Physical Examinations and Updated Physical Examinations

A full physical examination will be performed for those subjects that enroll in this study greater than one week following completion of the previous blinded study during the baseline visit by a qualified, licensed Doctor of Medicine (MD), Doctor of Osteopathy (DO), or physician assistant (PA). An updated physical examination will be performed for all subjects that enroll in this study at the Week 2 visit, Month 1 visit, Month 3 visit, Month 6 visit, Month 9 visit, Month 12 visit and every 6 month visit thereafter. At an End-of-Study visit, if a subject withdraws or is terminated from the study, a full physical examination will be performed.

A review of systems (ROS) will be included as part of the physical examination procedures. The ROS should include:

- Skin, hematological, cardiovascular, pulmonary, gastrointestinal, reproductive, neurological, psychiatric, lymphatic, endocrine, musculoskeletal, and/or drug allergies.
- Particular emphasis should be placed on careful elucidation of hematological, cardiac and cardiovascular, neurological and psychiatric conditions.

Findings will be documented in the subject's medical record and on the appropriate eCRF pages. Any significant changes from Day 1 (Baseline) are to be recorded during the updated physical examination and on the adverse event page for those subjects that enroll greater than one week following completion of previous study. Any significant changes from the last visit of the previous study are to be recorded during the updated physical examination and on the adverse event page for those subjects that enroll within one week following completion of previous study.

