12.1.4. Physical Examinations

Subjects who enroll in the study greater than one week following completion of the previous study will undergo a full physical examination at Day 1 (Baseline). All subjects in the study will undergo an updated physical examination at every study visit. A full physical examination will be conducted for all subjects who withdraw or are terminated from the study at an End-of-Study visit. Physical examination data will be included in data listings and reviewed for any clinically significant abnormalities.

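### SAP 5.13.8 pools change-recording update exams with full exit exams in one normal/abnormal table, so its percentages may move with exam type and with the share of subjects leaving

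*SAP*

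**What the plan says.** SAP 5.13.8 gives one sentence of analysis: "Physical examination results (normal, abnormal) will be summarized in a frequency table by body system by time period". A listing of abnormal findings by body system, with clinical significance and a comment, accompanies the table.

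The protocol describes two kinds of exam:

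- **Scheduled on-study visits** (Week 2, Months 1, 3, 6, 9 and 12, then every six months). Table 1, footnote 3 says the exam "will be an update to the full physical examination conducted during either the last visit of the previous study or at Baseline of this study". Section 6.2.2 adds, for subjects entering more than one week after the core study: "Any significant changes from Day 1 (Baseline) are to be recorded during the updated physical examination and on the adverse event page". For those entering within one week, the reference is the last visit of the previous study.
- **Exit.** Section 6.2.2: "At an End-of-Study visit, if a subject withdraws or is terminated from the study, a full physical examination will be performed".

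A full exam at Day 1 of this study is done only for the later entrants. For the others, the SAP definition of Baseline takes the value from the core study.

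Protocol 12.1.4 plans no frequency table: "Physical examination data will be included in data listings and reviewed for any clinically significant abnormalities". SAP 5.4.2 names physical examinations among the assessments whose within-period rules are set out in Section 5.13. Section 5.13.8 contains no such rule and no denominator.

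**The concern.** A normal/abnormal count by period is comparable across periods only if every exam in it answers the same question. A full exam asks what is abnormal now. An update asks what has changed significantly since the reference exam. A long-standing abnormality is recorded at the reference exam, may or may not reappear at updates, and is due to be recorded again at the exit exam.

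The one post-baseline full exam is also tied to leaving the study. A period in which many subjects leave therefore contains more full exams than one in which few do.

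Protocol 6.1 lists physical examinations among the measures of the primary safety objective. In a single-arm study a reader will naturally compare baseline with each period, and one period with the next. Those are the comparisons that mixed exam types can distort. The effect should be most visible at the interim snapshot of 13 December 2013 (SAP 5.12), when ongoing subjects have no exit exam.

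**Working it through.** The documents give no abnormality rate or expected figure for this table, so there is nothing to reproduce. I checked three things.

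**1. Size of the distortion when no patient changes.** Let

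- p = true prevalence of abnormality in a body system, constant over time;
- w = share of subjects in a period whose exam is the full End-of-Study exam;
- c = share of standing abnormalities that an update still records as abnormal.

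All three are my assumptions; the documents give none of them. A full exam at baseline shows p. A later period shows

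w × p + (1 − w) × c × p.

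For p = 50%, c = 0.1, w = 5%: 0.05 × 0.50 + 0.95 × 0.1 × 0.50 = 0.025 + 0.0475 = 7.25%. The other cases follow in the same way:

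| p (baseline) | c | w = 5% | w = 15% | w = 30% |
|---|---|---|---|---|
| 50% | 0.1 | 7.25% | 11.75% | 18.5% |
| 50% | 0.5 | 26.25% | 28.75% | 32.5% |
| 50% | 1.0 | 50% | 50% | 50% |
| 20% | 0.1 | 2.9% | 4.7% | 7.4% |

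With c below 1 the figure drops after baseline and then rises with w. With c = 1 it equals the baseline figure for every w.

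**2. What the missing within-period rule leaves open.** Counting nominal visit days, the SAP Table 2 periods contain 2, 1, 1 and 2 scheduled updates for days 2–28, 29–91, 92–183 and 184–365. For years 2, 3 and 4 the counts are 2, 2, 2 on the Amendment 6 schedule, and 4, 5, 4 on the three-monthly schedule that preceded it (SAP 2.2). Suppose one abnormal exam is enough to count, and assume an independent 5% chance per exam. The period figure is then 1 − 0.95^k: 5.0% for k = 1, 9.8% for k = 2, 18.5% for k = 4 and 22.6% for k = 5. The choice of rule therefore matters. Neighbouring sections state theirs: highest and lowest values for laboratory tests, vital signs and ECG, at least one clinically significant record for ECG interpretation, and the worst score for UPDRS.

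**3. The same no-change scenario under a baseline-normal count.** Restrict to subjects normal in that system at the reference full exam. They have no standing abnormality to carry forward or omit, so with no change in any patient the count is 0% for every w and c.

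**The case against.** The strongest reply is that the distortion depends on eCRF coding that the documents do not give. Section 6.2.2 says significant changes are to be recorded; it does not say unchanged findings are left off. It also says findings go on the appropriate eCRF pages and makes a review of systems part of the exam procedures without limiting it to full exams. If sites carry old findings forward, there is no artefact. This stands, and the conclusion has to be conditional.

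The second reply also stands. Significant changes found at updates go to the adverse event page as well, and treatment-emergent events are tabulated by period (SAP 5.13.1). Abnormal findings are listed. Vital signs, weight, ECG and UPDRS have their own analyses. A new significant finding has other routes into the report.

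A reader might infer that the table cannot show new findings. That does not follow: if updates record only changes, an abnormal entry at an update is itself a change. The most that can be said is that exit exams mix standing findings in with it.

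A reader might also infer that the SAP contradicts Protocol 12.1.4. It keeps the listing and adds a table, and Protocol 10 leaves detailed methods to the SAP. The table is an addition that SAP Section 6 does not mention, not a conflict.

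Finally, the End-of-Study visit is scheduled whenever a subject's enrolment ends (Protocol 3.6.2.5). At final analysis exit exams may therefore cover most subjects, although they still fall only in the period in which each subject leaves.

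**Conclusion.** The point holds in conditional form. SAP 5.13.8 pools two exam types, states no coding rule for unchanged findings, no within-period rule and no denominator, and makes no comparison with baseline. The abnormal percentages can therefore differ from baseline and between periods because of exam type and the share of subjects leaving.

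The size runs from nothing (full carry-forward) to a large drop. In the illustration, a constant 50% prints as 26.25% to 32.5% if half of standing abnormalities are carried forward, and as 7.25% to 18.5% if a tenth are. These figures rest on assumed values of p, w and c.

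It is tempting to go further and say that the percentages reflect exam type and withdrawal rather than drug effect. The documents do not support that: the coding is not stated, and no by-period percentage in a single-arm descriptive study isolates a drug effect anyway.

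The consequence is limited to one descriptive table. It is still worth correcting, because a better table is available under either coding and costs little.

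**What to change.** In SAP 5.13.8, replace the pooled normal/abnormal table with:

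1. By body system and Table 2 period, the number and percentage of subjects with an abnormal finding among those normal in that system at the reference full exam (Day 1, or the last core-study visit for entry within one week). Count a subject once per period if any exam in it shows an abnormality. The denominator is those baseline-normal subjects who were examined in that period.
2. A baseline to End-of-Study shift table by body system for subjects with both full exams.
3. The existing listing, which covers worsening of abnormalities already present at baseline.

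The SAP already works this way elsewhere: markedly abnormal laboratory values are also shown for subjects with normal baseline (5.13.3), and orthostatic hypotension is counted among subjects without it at baseline (5.13.4.2).

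The cost is SAP wording and one table to reprogram. Three limits remain. Worsening of an existing abnormality is not counted in table 1; the fields described in 5.13.8 include no flag for it. The shift table covers only subjects who left and had the End-of-Study exam. Counting any abnormal exam still depends on how many exams a period holds, so figures after Month 12 should be read with the Amendment 6 change in visit frequency in mind.
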